Null hypotheses to be tested:

1. That there is no statistically significant difference in gross motor function as measured using the North Star Ambulatory Assessment (NSAA) pre- and post-intervention.
2. That there is no statistically significant difference in functional abilities as measured using Pediatric Evaluation of Disability Inventory (PEDI) pre- and post-intervention.
3. That there is no statistically significant difference in postural control as measured using Segmental Assessment of Trunk Control (SATCo) pre- and post-intervention
4. That there is no statistically significant difference in sub-maximal exercise capacity as measured using the 2-minute walk test (2MWT) pre- and post-intervention.
5. That there is no statistically significant difference in body composition and bone mineral density as measured using dual X-ray absorptiometry (DXA) pre- and post-intervention.

Methodology

This feasibility study aims to examine the safety of the WBVT on children with type III SMA.

Children with type III SMA are targeted as they have adequate independence living in the community but still experience early fatigue during normal level of exercises due to the nature of their condition. They are at high risk of suffering from complications due to compromised mobility such as osteopenia, early loss of ambulation when compared with their healthy peers.

Intervention protocol

The WBVT will be performed on the Galileo™ Med L Plus (Novotech Medical GmbH) with the study participants standing with both knees flexed at least 20 degrees. The vibration frequency and duration will be increased over 5 days to the maximum of 3 minutes of 24 to 25 Hz with a peak to peak amplitude of 4mm. The participants of the intervention group will undergo the WBVT 1 session per day, 3 days per week for 4 weeks. The whole WBVT session will last 18 minutes with 9 minutes of vibration. This intervention regime is based on the recommended dosage to improve bone mineral density in children with physical disabilities in a systematic review on previous relevant literature (Matute-Llorente et al 2014). The intervention regime is as follows:

Day	Vibration 1	Rest 1	Vibration 2	Rest 2	Vibration 3	Rest 3
1st	1 min; 12Hz	3 min	1 min; 12Hz	3 min	1 min; 15Hz	3 min
2nd	1 min; 15Hz	3 min	1 min; 15Hz	3 min	2 min; 15Hz	3 min
3th	2 min; 15Hz	3 min	3 min; 15Hz	3 min	3 min; 15Hz	3 min
4th	2 min; 24-25Hz	3 min	2 min; 24-25Hz	3 min	2 min; 24-25Hz	3 min

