>5th	3 min; 24-25Hz	3 min	3 min; 24-25Hz	3 min	3 min; 24-25Hz	3 min

The participants will perform mini-squats (knee flexion from 20 to 40 degrees) during Vibrations 1 and 3 and weight-shifting between right and left legs during Vibration 2 on the vibration platform under the supervision of a research assistant, who will be trained by the PI prior to the commencement of the study. All treatment sessions will be conducted at the Hong Kong Polytechnic University Rehabilitation Clinic as most of children and adolescents with SMA study in main-stream schools in Hong Kong.

Participants:

10 children with type III SMA aged from 6 to 18 years will be recruited. The age range is extended aiming to increase the number of recruitment due to the rarity of the condition. All participants will continue their usual intervention regime, if any, during the study period. They are strongly encouraged not to participate any activities that may involve any total body vibration during the study period.

Inclusion criteria:

To be included in the study, children must:

1. Be able to stand on the vibration platform without support;
2. Be able to undertake clinical examination and DXA evaluation; and
3. Informed consent by the participant’s parent/ guardian.

Exclusion criteria:

1. There is a history of fracture within 8 weeks of enrolment of the present study and acute thrombosis, muscle or tendon inflammation, renal stones, discopathy or arthritis as reported by

their parent/ guardian.

2. There is a history of using any of the following medications, regardless of dose, for at least 1 month, within 3 months of enrolment into the present study: anabolic agents or growth hormone.

Outcome measures:

Assessments will be performed at baseline and after 4 weeks of the intervention. All outcome measures will be conducted on all study children, unless specified to children with specific diagnoses. They include:

1. Muscle strength

a) hand-held dynamometer will be used to measure muscle strength in hip flexors, hip extensors, hip abductors, knee extensors, knee flexors, ankle plantarflexors and dorsiflexors in standardised muscle testing positions (Clarkson and Gilewich 2000). Muscle strength will be reported in kilograms.

2. Functional abilities

a) North Star Ambulatory Assessment (NSAA) will be used to examine the gross motor function of the participants (Mayhew et al 2011, Scott et al 2012).

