b) 2-minute walk test (2MWT) will be used to assess submaximal exercise capacity (Pin 2014, Pin and Choi 2016). Distance covered in 2MWT will be measured by a distance-measuring trundle wheel in metres.

c) Range of movements in hip flexion, extension and abduction, knee flexion and extensions and ankle dorsiflexion and plantarflexion will be measured in standardised positions (Clarkson and Gilewich 2000).

d) Segmental Assessment of Trunk Control (SATCo) to assess the segment trunk control (Butler et al 2010).

e) Pediatric Evaluation of Disability Inventory (PEDI) (Haley et al 1992) to assess functional capacities in the domains of daily activities, mobility and social/cognitive function. A validated Chinese version will be used (Chen et al 2009).

3. Bone mineral density

a) Dual Energy X-ray Absorptiometry (DXA)- bone mineral content (BMC) and areal bone mineral density (aBMD) of the distal femur and total body will be measured. *Only if* it is not feasible to obtain the BMC and aBMD of the femur, BMD of the lumbar spine will be used. The effective radiation dose for these DXA studies will be <2 microSv, which is a very minimal dose of radiation (Houlihan and Stevenson 2009). All participants will have DXA done in a private service as bone density examination is not routine for the children with motor disabilities in Hong Kong.

b) Anthropometry at baseline and 4 weeks including standing height and weight. Body mass index (BMI) will be calculated and converted into a z-score.

4. Parental satisfaction

a) Parental/ participant questionnaire to record present medications of their children, satisfaction or comments on the intervention regime by children/ parents of the intervention group.

b) Visual analogue scale of 0 to 10, in which 0 means no pain and 10 as extreme pain to assess pain or discomfort at rest and if any, pain or discomfort associated with the intervention as reported by the children and/or parents.

c) A log of compliance and comments during the intervention.

Statistical analysis plan

Due to the small sample size, non-parametric tests will be used to analyse the results. All results will be reported in means and standard deviations. Wilcoxon Signed test will be used to

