compare all the outcome measures listed above (no. 1 to 3) before and after the intervention. Results of outcome measure no. 4 listed above will be reported in descriptive terms for the comments from the parents and/or from the participants and compliance/ comments during the intervention and Wilcoxon Signed test will also be used to compared the visual analogue score of discomfort before and after the intervention.

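### One before-after Wilcoxon test is planned for a pain VAS that holds two scores, one without a baseline, and with 10 children its result says little about safety

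*Combined protocol and SAP*

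**What the plan says.** Under Methodology the study gives itself a safety purpose: "This feasibility study aims to examine the safety of the WBVT on children with type III SMA". The planned size is stated under Participants: "10 children with type III SMA aged from 6 to 18 years will be recruited".

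The pain scale is item 4(b) of the Outcome measures, under the label of parental satisfaction. It runs from 0 to 10 and is used "to assess pain or discomfort at rest and if any, pain or discomfort associated with the intervention as reported by the children and/or parents". The general schedule for outcomes is "Assessments will be performed at baseline and after 4 weeks of the intervention". Item 4(c) adds "A log of compliance and comments during the intervention".

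The Statistical analysis plan explains its choice of tests: "Due to the small sample size, non-parametric tests will be used to analyse the results". Results are to be summarised as means and standard deviations. Comments and compliance are to be described. For the pain scale, "Wilcoxon Signed test will also be used to compared the visual analogue score of discomfort before and after the intervention".

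The plan gives no significance level, sidedness, exact or asymptotic version, or rule for zero changes and ties. It names no count of children with new or worse pain and no safety criterion. None of the five null hypotheses concerns pain.

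**The concern.** The analysis refers to a single discomfort score, but item 4(b) defines two. A child cannot have pain from the vibration before the first session, so that score has no first member of a pair. Unless the plan says which score is meant, an analyst must choose later, perhaps with the data in view. One possible choice would pair rest pain at baseline with intervention-associated pain afterwards, which is a difference between two unlike quantities.

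The second problem is what the result can show. The scale is the only scored measure of pain or discomfort in a study with a safety aim, and the Wilcoxon test is the only analysis named for it beyond mean and standard deviation. With 10 children, a non-significant p-value is compatible with new pain in a substantial share of them. The quantity a feasibility study needs, how many children had pain and how bad it was, is not among the planned results.

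**Working it through.** **Which score can be paired**

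| Score in item 4(b) | Value at baseline | Value after 4 weeks | Paired test defined? |
|---|---|---|---|
| Pain at rest | yes | yes | yes |
| Pain associated with the intervention | none possible | yes | no |

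Setting the missing baseline to 0 by convention does not help. Every change would then be zero or positive, and a null hypothesis of changes symmetric about zero would hold only if no child had any pain.

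**What the test can detect**

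Inputs from the documents: n = 10, one group, signed-rank test of before versus after. Assumptions, because the plan is silent: alpha 0.05, two-sided, exact. Other versions are shown as a range. The plan has no power or sample-size figure to reproduce.

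Let k children worsen and the other 10 − k stay unchanged. All k signs agree, so the exact two-sided p is 2/2^k, whatever the size of the changes. Significance needs 2^k > 40, so k ≥ 6.

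| k of 10 worse | Exact two-sided | Exact one-sided | Normal, two-sided, uncorrected (distinct / all tied) | Normal, two-sided, continuity-corrected (distinct / all tied) |
|---|---|---|---|---|
| 3 | 0.25 | 0.125 | 0.109 / 0.083 | 0.181 / 0.149 |
| 4 | 0.125 | 0.0625 | 0.068 / 0.046 | 0.100 / 0.072 |
| 5 | 0.0625 | 0.031 | 0.043 / 0.025 | 0.059 / 0.037 |
| 6 | 0.031 | 0.016 | 0.028 / 0.014 | 0.036 / 0.020 |

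- Five of 10 is non-significant under the exact two-sided test but significant under several other versions.
- Three of 10 is non-significant in every version in the table. A one-sided normal approximation is not tabulated; halving the smallest two-sided value gives 0.083/2 = 0.042, so that version could cross 0.05.
- Keeping the zero changes in the ranking (Pratt) leaves the exact p for k = 5 at 0.0625. Dropping zeros is therefore not the cause; unchanged children carry no sign under either rule.
- Severity does not help: five children going from 0 to 10 still give 0.0625.
- If some children improve, more worsening can go undetected. Eight worse and 2 improved can give an exact two-sided p as high as 0.43; 9 worse and 1 improved, as high as 0.084.

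If each child independently has risk π of new pain and none improves, the exact two-sided test is significant with probability P(X ≥ 6), X ~ Binomial(10, π): 0.047 for π = 0.3, 0.166 for 0.4 and 0.377 for 0.5.

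**What a count would show**

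Exact (Clopper-Pearson) 95% intervals:

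- 0/10: upper limit 1 − 0.025^(1/10) = 30.8%
- 3/10: 6.7% to 65.2%
- 5/10: 18.7% to 81.3%

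**The case against.** The best defence is that the sentence in the analysis plan can reasonably be read as pain at rest, which is validly paired, with intervention-associated pain recorded only if it occurs. That reading is possible, but the plan does not state it, and it would leave intervention-associated pain with no named analysis beyond means and standard deviations. The need to specify stands.

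A reader might also infer more than the documents support:

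- *That the plan will declare the therapy safe if this test is non-significant.* It never says so. The scale sits under parental satisfaction, no null hypothesis covers pain, and comments and compliance are also reported, so new pain could surface there. Free-text comments do not, however, give a defined rate.
- *That half the children could always develop pain without a significant result.* This depends on an exact two-sided test at 0.05, which is an assumption. That the answer changes with an unstated option is itself a reason to specify.
- *That pain during the sessions is missed altogether.* Item 4(b) asks about "pain or discomfort associated with the intervention as reported by the children and/or parents" and item 4(c) takes comments. What is missing is a stated schedule for scoring that pain.
- *That most children will score 0 at both visits, or that the rater will switch between child and parent.* The documents do not show that either will happen. The wording permits a change of rater, so noting who gave each score is sensible, but no bias can be quantified.

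It is also fair to say that low power at n = 10 affects every Wilcoxon test in the plan. It matters particularly here because absence of a difference is the reassuring result.

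**Conclusion.** The concern holds in limited form. The before-after test is undefined for intervention-associated pain, and the plan does not say which of the two scores it applies to; this follows from the text and needs no assumption. Pain at rest can properly be paired.

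The test is also a poor basis for the safety aim. Under an exact two-sided test at 0.05, at least 6 of 10 children must worsen, with none improving, before it is significant. Under the other versions tabulated the minimum is 4 to 6, and 3 of 10 never reaches significance. The detection probabilities further assume independent children and no improvement. This is a defect of specification and of the choice of summary, and it can be corrected before analysis.

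**What to change.** In the Statistical analysis plan:

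1. Name the two pain scores and analyse them separately.
2. Show pain at rest as individual paired baseline and 4-week values. If a Wilcoxon p-value is kept, label it descriptive and state sidedness, exact or asymptotic version, and the handling of zeros and ties.
3. Report intervention-associated pain as the number of children with any such pain, with an exact 95% confidence interval for the proportion, and give the maximum score for each affected child. State the denominator.
4. State that a non-significant Wilcoxon result will not be taken as evidence of safety.

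Where practical, enter an intervention-associated score in the log already planned under item 4(c) and note whether the child or the parent gave it. Two readings at every session by a fixed rater would be a larger step: 2 × 12 sessions (3 per week for 4 weeks) × 10 children = 240 scores. The analysis changes above do not depend on it.

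The cost is a few sentences of SAP text and a little more recording. The interval will show openly how little 10 children can exclude: even with no child affected, a true rate of up to about 31% remains compatible with the data.
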